4.2.3.3 Pharmacokinetic Endpoints

At the timepoints specified in the Trial Flow Chart (Section 6.0), whole blood samples will be collected for determination of plasma concentration of REL, imipenem, and CIL. These samples will support further evaluation of the PK profiles of these drugs by confirming that subjects achieve expected exposures, and will also aid in further assessment of the clinical relationship between REL plasma concentrations and efficacy against resistant isolates.

4.2.3.4 Future Biomedical Research

The Sponsor will conduct Future Biomedical Research on DNA (blood) specimens collected during this clinical trial. Importantly, a subject may participate in the main trial without participating in Future Biomedical Research portion of this study.

Such research is for biomarker testing to address emergent questions not described elsewhere in the protocol (as part of the main trial) and will only be conducted on specimens from appropriately consented subjects. The objective of collecting specimens for Future Biomedical Research is to explore and identify biomarkers that inform the scientific understanding of diseases and/or their therapeutic treatments. For instance, exploratory pharmacogenetic (PGt) studies may be performed if significant Pharmacokinetic/Pharmacodynamic (PK/PD) relationships are observed or adverse events are identified. Genomic markers of disease may also be investigated. Such retrospective pharmacogenetic studies will be conducted with appropriate biostatistical design and analysis and compared to PK/PD results or clinical outcomes. Any significant PGt relationships to outcome would require validation in future clinical trials. The overarching goal is to use such information to develop safer, more effective drugs/vaccines, and/or to ensure that subjects receive the correct dose of the correct drug/vaccine at the correct time. The details of this Future Biomedical Research sub-trial are presented in Section 12.2 - Collection and Management of Specimens for Future Biomedical Research. Additional informational material for institutional review boards/ethics committees (IRBs/ERCs) and investigational site staff is provided in Section 12.3.

4.3 Benefit/Risk

Subjects enrolled in this trial are generally hospitalized patients with multi-drug resistant infections requiring treatment with IV therapy. As discussed in Section 4.2, available treatment options for patients infected with resistant pathogens are limited. If randomized to receive IMI/REL, subjects can potentially benefit from treatment with this investigational agent specifically targeted for treatment of Gram-negative imipenem-resistant infections. Subjects randomized to the comparator arm will also receive a treatment regimen expected to be efficacious against these infections (see Section 4.2.2.6). Regardless of treatment assignment, the study has been designed to support prompt receipt of appropriate therapy for all eligible subjects. Typical treatment of hospitalized patients with any bacterial infection is decided based on *in vitro* susceptibility of pathogens isolated from an infection-site specimen. In order to support timely initiation of effective study therapy and thus reduce risk of treatment failure, *in vitro* susceptibility results confirming susceptibility for both the investigational and comparator agents in this trial is required prior to randomization. The Sponsor will provide susceptibility panels to all investigator sites to support this testing.

Although potentially more frequent than standard of care, the study procedures described in Section 6.0 (Trial Flow Chart) are generally typical procedures performed for this hospitalized patient population. Additional burden may be incurred due to visits following release from the hospital. However, the procedures performed at these visits are generally not likely to lead to significant harm (e.g., blood draws, urine collection, physical exam, vital signs). These procedures are necessary to support a robust evaluation of the safety and efficacy of the investigational drug with potential to support treatment of patients for whom no or limited alternative therapies are available.

Additional details regarding specific benefits and risks for subjects participating in this clinical trial may be found in the accompanying Investigators Brochure (IB) and Informed Consent documents.

5.0 METHODOLOGY

5.1 Entry Criteria

5.1.1 Diagnosis/Condition for Entry into the Trial

Male and female subjects who are at least 18 years of age and have an imipenem-resistant Gram-negative bacterial infection involving one of 3 primary infection types (HABP/VABP, cIAI, or cUTI) will be enrolled in this trial.

5.1.2 Subject Inclusion Criteria

5.1.2.1 Treatment Groups 1 and 2

In order to be eligible for participation in this trial, the subject must:

1. be ≥ 18 years of age on the day of signing informed consent at the randomization visit.

NOTE: Adults are the intended study population for this protocol. Subjects under the age of legal consent per a specific country's regulations should be excluded from participation in this study

2. require hospitalization and treatment with IV antibiotic therapy for a new, persistent (defined as inadequate response to current therapy or failure to improve as expected) or progressing (defined as clinically worsening despite treatment) bacterial infection with at least one of the following primary infection types:
 - Hospital-acquired bacterial pneumonia (HABP) or ventilator-associated bacterial pneumonia (VABP)
 - Complicated intra-abdominal infection (cIAI)
 - Complicated urinary tract infection (cUTI)

NOTE: Diagnostic criteria, including relevant radiographic, clinical and microbiological evidence, for each infection type are in Appendix 12.5.

3. has positive culture data obtained from the primary infection-site specimen collected within 1 week of study entry and at least one of the suspected causative pathogen(s) from that specimen meets all of the following criteria:
 - a. has been identified as a Gram-negative bacterium, AND
 - b. has culture-confirmed imipenem resistance (MIC of isolate is above the imipenem-susceptible breakpoint) based on panels provided by the Sponsor, AND
 - c. has culture-confirmed susceptibility to colistin (MIC of isolate is at or below the colistin-susceptible breakpoint) and to IMI/REL (MIC of isolate is at or below the imipenem-susceptible breakpoint) based on panels provided by the Sponsor.

4. agree to allow any bacterial isolates obtained from protocol-required specimens related to the current infection to be provided the Central Microbiology Reference Laboratory for study-related microbiological testing, long-term storage, and other future testing.
5. understand (or have a legal representative that understands) the study procedures, alternative treatments available, and risks involved with the study, and voluntarily agree to participate by giving written informed consent for the trial. The subject or legally acceptable representative may also provide consent for Future Biomedical Research. However, the subject may participate in the main trial without participating in Future Biomedical Research.
6. Meet one of the following categories:
 - a) The subject is a male who is not of reproductive potential, defined as a male who has azoospermia (whether due to having had a vasectomy or due to an underlying medical condition).
 - b) The subject is a female who is not of reproductive potential, defined as a female who either: (1) is postmenopausal (defined as at least 12 months with no menses in women ≥ 45 years of age); (2) has had a hysterectomy and/or bilateral oophorectomy, bilateral salpingectomy, or bilateral tubal ligation/occlusion at least 6 weeks prior to screening; OR (3) has a congenital or acquired condition that prevents childbearing.
 - c) The subject is a female or a male who is of reproductive potential and agrees to avoid becoming pregnant or impregnating a partner from the time of consent through completion of the study by complying with one of the following: (1) practice abstinence[†] from heterosexual activity OR (2) use (or have their partner use) acceptable contraception during heterosexual activity. Acceptable methods of contraception are[‡]:

Single method (one of the following is acceptable):

- non-hormonal intrauterine device (IUD)
- vasectomy of a female subject's male partner

Combination method (requires use of two of the following):

- diaphragm with spermicide (cannot be used in conjunction with cervical cap/spermicide)
- cervical cap with spermicide (nulliparous women only)
- contraceptive sponge (nulliparous women only)
- male condom or female condom (cannot be used together)
- hormonal contraceptive: oral contraceptive pill (estrogen/progestin pill or progestin-only pill), contraceptive skin patch, vaginal contraceptive ring, or subcutaneous contraceptive injection

[†]Abstinence (relative to heterosexual activity) can be used as the sole method of contraception if it is consistently employed as the subject's preferred and usual lifestyle

and if considered acceptable by local regulatory agencies and ERCs/IRBs. Periodic abstinence (e.g., calendar, ovulation, sympto-thermal, post-ovulation methods, etc.) and withdrawal are not acceptable methods of contraception.

‡If a contraceptive method listed above is restricted by local regulations/guidelines, then it does not qualify as an acceptable method of contraception for subjects participating at sites in this country/region.

5.1.2.2 Open-Label, Treatment Group 3

In order to be eligible for participation in this trial, the subject must:

1. be ≥ 18 years of age on the day of signing informed consent at the randomization visit.

NOTE: Adults are the intended study population for this protocol. Subjects under the age of legal consent per a specific country's regulations should be excluded from participation in this study.

2. require hospitalization and treatment with IV antibiotic therapy for a new, persistent (defined as inadequate response to current therapy or failure to improve as expected) or progressing (defined as clinically worsening despite treatment) bacterial infection with at least one of the following primary infection types:

- Hospital-acquired bacterial pneumonia (HABP) or ventilator-associated bacterial pneumonia (VABP)
- Complicated intra-abdominal infection (cIAI)
- Complicated urinary tract infection (cUTI)

NOTE: Diagnostic criteria, including relevant radiographic, clinical and microbiological evidence, for each infection type are in Appendix 12.5.

3. have positive culture data obtained from the primary infection-site specimen collected within 1 week of study entry and at least one of the suspected causative pathogen(s) from that specimen meets all of the following criteria:
 - a. has been identified as a Gram-negative bacterium, AND
 - b. has culture-confirmed imipenem resistance (MIC of isolate is above the imipenem-susceptible breakpoint) and colistin resistance (MIC of isolate is above the colistin-susceptible breakpoint) based on panels provided by the Sponsor, AND
 - c. has culture-confirmed susceptibility to IMI/REL (MIC of isolate is at or below the imipenem-susceptible breakpoint) based on panels provided by the Sponsor.
4. agree to allow any bacterial isolates obtained from protocol-required specimens related to the current infection be provided to the Central Microbiology Reference Laboratory for study-related microbiological testing, long-term storage, and other future testing.

5. understand (or have a legal representative that understands) the study procedures, alternative treatments available, and risks involved with the study, and voluntarily agree to participate by giving written informed consent for the trial. The subject (or legally acceptable representative) may also provide consent for Future Biomedical Research. However, the subject may participate in the main trial without participating in Future Biomedical Research.
6. Meet one of the following categories:
 - a) The subject is a male who is not of reproductive potential, defined as a male who has azoospermia (whether due to having had a vasectomy or due to an underlying medical condition).
 - b) The subject is a female who is not of reproductive potential, defined as a female who either: (1) is postmenopausal (defined as at least 12 months with no menses in women ≥ 45 years of age); (2) has had a hysterectomy and/or bilateral oophorectomy, bilateral salpingectomy, or bilateral tubal ligation/occlusion at least 6 weeks prior to screening; OR (3) has a congenital or acquired condition that prevents childbearing.
 - c) The subject is a female or a male who is of reproductive potential and agrees to avoid becoming pregnant or impregnating a partner from the time of consent through completion of the study by complying with one of the following: (1) practice abstinence[†] from heterosexual activity OR (2) use (or have their partner use) acceptable contraception during heterosexual activity. Acceptable methods of contraception are[‡]:

Single method (one of the following is acceptable):

- non-hormonal intrauterine device (IUD)
- vasectomy of a female subject's male partner

Combination method (requires use of two of the following):

- diaphragm with spermicide (cannot be used in conjunction with cervical cap/spermicide)
- cervical cap with spermicide (nulliparous women only)
- contraceptive sponge (nulliparous women only)
- male condom or female condom (cannot be used together)
- hormonal contraceptive: oral contraceptive pill (estrogen/progestin pill or progestin-only pill), contraceptive skin patch, vaginal contraceptive ring, or subcutaneous contraceptive injection

[†]Abstinence (relative to heterosexual activity) can be used as the sole method of contraception if it is consistently employed as the subject's preferred and usual lifestyle and if considered acceptable by local regulatory agencies and ERCs/IRBs. Periodic abstinence (e.g., calendar, ovulation, sympto-thermal, post-ovulation methods, etc.) and withdrawal are not acceptable methods of contraception.

‡If a contraceptive method listed above is restricted by local regulations/guidelines, then it does not qualify as an acceptable method of contraception for subjects participating at sites in this country/region.

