4.1.1 Pharmaceutical and Therapeutic Background

MK-7655 (relebactam) is a parenteral (IV), small-molecule β -lactamase inhibitor (BLI) which is being developed as a fixed dose combination in a single vial with imipenem/cilastatin (referred to as IMI) for the treatment of infections caused by Gram-negative bacteria. Throughout this document the fixed dose combination of imipenem/cilastatin/relebactam (MK-7655A) will be referred to as IMI/REL. β -lactam antibiotics (penicillins, cephalosporins, carbapenems, and monobactams) are among the most frequently used antimicrobial agents in clinical practice. The unrelenting development of resistance to these β -lactam antibiotics by the production of β -lactamases is the most important resistance mechanism among Gram-negative bacteria and poses an ongoing threat to the clinical utility of all β -lactams. Therefore, there is an urgent need for new BLIs that can be combined with existing β -lactam antibiotics to protect against hydrolysis by one or more of the four classes (A, B, C and D) of β -lactamase enzymes.

Relebactam (REL) represents a new generation of BLIs to combat evolving clinical resistance and to maintain the usefulness of the β -lactam class of antibiotics. REL is a dual Ambler Class A/Class C BLI. This BLI is highly potent for AmpC, a common Class C β -lactamase encountered in many bacteria, most predominantly *Pseudomonas aeruginosa*. REL is also active against the Class A β -lactamases, including the *Klebsiella pneumoniae* carbapenemase (KPC) present in some Enterobacteriaceae, including *Klebsiella* strains. REL has no activity against the Class B metallo- β -lactamases (including NDM-1, IMP, or VIM-containing strains) or Class D β -lactamases (including OXA-producing strains).

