5.1.3 Subject Exclusion Criteria

5.1.3.1 Treatment Groups 1 and 2

The subject must be excluded from participating in the trial if the subject:

1. has an APACHE II score >30 at screening
2. has an infection in which any of the causative pathogens are any of the following:
 - Imipenem-resistant *Acinetobacter* spp.
 - suspected Class B metallo-beta-lactamase-producing bacteria (including NDM-1, IMP or VIM-containing strains)
3. has a concurrent infection that would interfere with evaluation of response to the study antibiotics (IMI/REL or CMS + IMI), including any of the following:
 - endocarditis
 - osteomyelitis
 - meningitis
 - prosthetic joint infection
 - active pulmonary tuberculosis
 - a disseminated fungal infection
4. has received treatment with any form of systemic colistin for > 24 hours within the 72 hours immediately prior to initiation of study therapy.
5. has HABP/VABP caused by an obstructive process, including lung cancer (or other malignancy metastatic to the lungs resulting in pulmonary obstruction) or other known obstruction.
6. has cUTI which meets any of the following:
 - complete obstruction of any portion of the urinary tract (requiring a permanent indwelling urinary catheter or instrumentation)
 - known ileal loop
 - intractable vesico-ureteral reflux
 - presence of indwelling urinary catheter which cannot be removed at study entry

NOTE: All indwelling urinary catheters must be removed prior to the start of IV therapy. Unless medically necessary, it is recommended that an indwelling urinary catheter not be reinserted while on IV study therapy.

7. has a history of serious allergy, hypersensitivity (e.g., anaphylaxis), or any serious reaction to any of the following:

- any carbapenem, cephalosporin, penicillin, or other β -lactam agent
- colistimethate sodium (colistin) or to polymyxin B
- other β -lactamase inhibitors (e.g., tazobactam, sulbactam, clavulanic acid, avibactam)

NOTE: Subjects with a history of mild rash to penicillins or other β -lactams may be enrolled and closely monitored.

8. is a female who is pregnant or is expecting to conceive (or is a male partner of a female who is expecting to conceive), is breastfeeding, or plans to breastfeed prior to completion of the study.

9. has any of the following medical conditions at screening:

- history of a seizure disorder (requiring ongoing treatment with anti-convulsive therapy or prior treatment with anti-convulsive therapy within the last 3 years)
- myasthenia gravis

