6. A new imipenem-resistant Gram-negative bacterium is isolated from an infection site during study therapy and is not susceptible to IMI/REL and colistin.

NOTE: Since subjects enrolled into Treatment Group 3 are required to have a colistin-resistant infection at randomization, development of a new colistin-resistant infection would not require discontinuation.

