8.2.4 Analysis Populations

8.2.4.1 Efficacy Analysis Populations

The microbiological modified Intention to Treat (mMITT) population will serve as the primary population for efficacy analyses in this study. The mMITT population is defined as all randomized subjects who receive at least one dose of each study drug within a given IV study therapy regimen, and who have a baseline bacterial pathogen meeting inclusion criterion #3. In the case of a polymicrobial infection, at least one pathogen must satisfy the requirements of inclusion criterion #3, and all pathogens identified at the baseline time point must be susceptible to both IMI/REL and colistin. Subjects will be included in the treatment group to which they are randomized for the analysis of efficacy data using the mMITT population.

The per-protocol (PP) population will serve as the secondary population for the primary efficacy endpoint (proportion of subjects with a favorable overall response as assessed for each of the three infection types). The PP population is a subset of the mMITT population who also meet the following criteria:

1. Meet important diagnostic criteria for entry into the study,

2. Have no significant deviation from the protocol that could impact the assessment of efficacy, and
3. Receive the minimum duration of IV study therapy as detailed in Section 5.2

The final exclusion criteria and list of patients who will be excluded from the PP population will be documented prior to unblinding.

Details on the approach to handling missing data are provided in Section 8.2.5 (Statistical Methods).

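### Entry to Groups 1 and 2 needs one pathogen susceptible to both agents, but mMITT needs all of them, so some subjects can be randomised and treated yet never count in the primary analysis

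*Combined protocol and SAP*

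**What the plan says.** **Entry.** For Groups 1 and 2, inclusion criterion 3 (Section 5.1.2.1) is met when "at least one of the suspected causative pathogen(s) from that specimen meets all of the following criteria". The criteria are Gram-negative identity, imipenem resistance, and susceptibility to colistin and to IMI/REL on the Sponsor's panel. Nothing is required of a second pathogen.

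**Exclusion.** Criterion 2 (Section 5.1.3.1) does look beyond the qualifying isolate. It applies if the subject "has an infection in which any of the causative pathogens are any of the following", but lists two items only: imipenem-resistant Acinetobacter, and "suspected Class B metallo-beta-lactamase-producing bacteria (including NDM-1, IMP or VIM-containing strains"). Section 4.1.1 says "REL has no activity against the Class B" enzymes, and the same sentence extends this to Class D (OXA) producers, which exclusion 2 does not name. Section 4.1.3 lists Gram-negatives that colistin does not cover, among them Proteus, Providencia and Serratia.

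**Benefit/risk.** Section 4.3 says that "susceptibility results confirming susceptibility for both the investigational and comparator agents in this trial is required prior to randomization". Section 4.2.2.3 speaks of confirmed colistin susceptibility of the pathogens, in the plural. Section 1.0 describes the enrolled infections as susceptible to both agents.

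**Stopping.** Section 5.8 lists, among mandatory reasons to stop IV study therapy, item 6: "A new imipenem-resistant Gram-negative bacterium is isolated from an infection site during study therapy and is not susceptible to IMI/REL and colistin". Its note exempts Group 3 from stopping for a new colistin-resistant infection.

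**Analysis set.** For a polymicrobial infection, mMITT requires that "all pathogens identified at the baseline time point must be susceptible to both IMI/REL and colistin" (Section 8.2.4.1; also Section 8.1.1 and Table 16).

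**Group 3.** Section 5.1.2.2, criterion 3, again asks for one qualifying pathogen, this time one that "has culture-confirmed imipenem resistance (MIC of isolate is above the imipenem-susceptible breakpoint) and colistin resistance" and is IMI/REL-susceptible.

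**The concern.** The plan applies three different tests to what may be the same organism. At entry, one isolate must pass. During therapy, a newly isolated imipenem-resistant Gram-negative is judged on its own susceptibility, and failing is a mandatory stop. For mMITT, every baseline pathogen must pass. A subject who has one qualifying isolate and one that fails meets the listed entry criteria and is then barred from the primary population by a result that was available before randomisation.

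First at stake is exposure. The subject may be assigned a regimen that tests as inactive against one causative pathogen, while Section 5.5 prohibits adding non-study Gram-negative cover. The benefit/risk argument in Section 4.3 rests on this not happening. Second is information: the subject contributes to safety but cannot contribute to the primary estimate. Third is allocation: a subject carrying both isolate types satisfies the culture criteria of the randomised cohort and of the open-label cohort, and no rule says which takes precedence. Section 5.4 does write such a rule for subjects with several infection sites.

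**Working it through.** No figure in the plan needs reproducing for the main point. The check is whether the rules agree on the same subject.

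**Step 1. Possible profiles of a second causative isolate.** Take a subject whose first isolate qualifies. Let the second be an imipenem-resistant Gram-negative outside exclusion 2. S means susceptible and NS not susceptible on the panel.

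| Second isolate: IMI/REL, colistin | Bars entry? | Arm that does not cover it in vitro | mMITT? | New on therapy: stop if 'and' means either | Stop if 'and' means both |
|---|---|---|---|---|---|
| S, S | No | Neither | Yes | No | No |
| NS, S | No | Group 1 | No | Yes | No |
| S, NS | No | Group 2 | No | Yes | No |
| NS, NS | No | Both | No | Yes | Yes |

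The last three rows all pass entry and all fail mMITT. In the third row neither Group 2 component tests as active, because the isolate is resistant to imipenem as well as to colistin. With 2:1 allocation, a second-row subject has a 2 in 3 chance of the arm that does not cover the isolate, and a third-row subject 1 in 3. For a fourth-row subject it is certain.

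**Step 2. The stopping wording.** Item 6 of Section 5.8 can mean not susceptible to either agent or not susceptible to both. The note that exempts Group 3 from stopping for colistin resistance would be unnecessary if colistin resistance alone never triggered the rule, so it supports 'either'. Under 'both', the mismatch with entry remains for the fourth row only. Item 6 concerns a new isolate, so a co-pathogen present at baseline does not trigger it.

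**Step 3. Overlap of cohorts.** The third-row subject has one isolate meeting criterion 3 of Section 5.1.2.1 and one meeting criterion 3 of Section 5.1.2.2. Both are satisfied.

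**Step 4. An adjoining profile.** A co-isolate susceptible to imipenem but resistant to colistin is covered by imipenem in both regimens, yet the mMITT wording drops this subject too.

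**Step 5. Size.** The plan randomises about 54 to obtain at least 45 in mMITT. That is 54 − 45 = 9, or 9/54 = 16.7%, for losses of every kind (18 − 15 = 3 per stratum). No loss rate is stated; 45/(1 − 1/6) = 54 only restates the plan's two numbers. Let q be the share of randomised subjects in the last three rows. The documents give no value, so q is purely an assumption. If these losses come on top of the implied 1/6, the number to randomise is 45/[(1 − q) × 5/6]:

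- q = 5%: 56.8, so 57 (3 more than 54)
- q = 10%: 60 (6 more)
- q = 20%: 67.5, so 68 (14 more)

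**The case against.** Co-pathogens are not ignored at entry. Footnote q of the Trial Flow Chart and Section 7.1.3.2.1 require identification and panel susceptibility of the suspected causative pathogens before randomisation. Exclusion 10 bars anyone expected to need non-study agents covering the Gram-negatives of interest, so an investigator who means to treat an uncovered organism cannot enrol that subject. Exclusion 13 allows refusal for added risk. After entry, item 5 of Section 5.8 requires discontinuation when the investigator judges it in the subject's best interest, including a need for alternative antibacterial therapy. Section 4.3 does not say that every pathogen must be susceptible, and item 6 of Section 5.8 is about new isolates.

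Most of this stands, and it narrows the point. The isolates are tested, but only one has to pass. Exclusions 10 and 13 and stopping item 5 depend on judgement; none is a susceptibility rule. Read literally, criterion 3 may satisfy Section 4.3, but a benefit/risk argument about timely effective therapy has little force if a second causative organism may be uncovered.

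It is also fair that colistin resistance is expected to be uncommon: Section 2.1 anticipates only 5 to 10 Group 3 subjects. The third-row subject additionally needs a colistin-susceptible, imipenem-resistant isolate, so that route may be rare.

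**Conclusion.** The inconsistency is real. Entry, benefit/risk, stopping and mMITT rules treat a second imipenem-resistant Gram-negative differently, and a subject can be randomised and exposed who, by rule and on information already in hand, cannot count in the primary analysis. This rests on the wording alone. The part concerning stopping also rests on reading 'and' as 'either', which the Group 3 note supports but does not settle.

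Three stronger conclusions might be inferred and are not supported.

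- **That the plan has room for 9 losses which this route could use up.** Sections 2.1 and 5.4 allow enrolment beyond 54 to reach the mMITT target, so 9 is not a ceiling, and there is no documented frequency to set against it. The cost would be more subjects exposed, not necessarily a missed target.
- **That the treatment comparison is biased.** The susceptibility part of mMITT depends on baseline isolates and is applied alike to both arms.
- **That sites could distort the primary result by choosing Group 3.** That choice precedes randomisation, the subjects concerned are outside mMITT anyway, and Group 3 is summarised separately. The overlap is a missing rule, not a source of bias in the mMITT estimates.

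**What to change.** Reconcile the entry criteria (Sections 5.1.2.1, 5.1.2.2, 5.1.3.1 and 5.1.3.2) with Sections 4.3, 5.8 and 8.2.4.1:

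1. For Groups 1 and 2, apply at entry the all-pathogen susceptibility condition already in the mMITT definition, for imipenem-resistant Gram-negative causative pathogens, using the pre-randomisation panel results. Check the Group 3 criteria for the same gap in IMI/REL susceptibility.
2. State which cohort's criteria govern when a subject meets the culture criteria of both. The choice is for the sponsor.
3. Clarify whether 'and' in item 6 of Section 5.8 means either agent or both, and reconcile it with entry.
4. Say how imipenem-susceptible, colistin-resistant co-isolates are handled. Item 1 leaves them eligible, while mMITT drops them.

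The cost is a few lines of text and no new testing. Slightly fewer subjects would be randomised and slightly less safety data collected, but none of those removed from Groups 1 and 2 could have counted toward the 45. Organisms first found in the Day 1 culture would still be missed at entry, so the mMITT rule remains necessary.
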